Cerebrolysin as an Early Add-on to Reperfusion Therapy: Risk of Hemorrhagic Transformation after Ischemic Stroke (CEREHETIS). A Prospective, Randomized, Active-Control, Multicenter Pilot Study

Clinical Trial Protocol

Date: 30 April 2018

PROTOCOL SYNOPSYS

Sponsor None

Final Product Cerebrolysin

Active Ingredient Cerebrolysin concentrate

Clinical Trial Title

Cerebrolysin as an Early Add-on to Reperfusion Therapy: Risk of Hemorrhagic Transformation after Ischemic Stroke (CEREHETIS). A Prospective, Randomized, Active-Control, Multicenter Pilot Study

Primary Investigator

[name]

Clinical Trial Centers

- 1. Interregional Clinical Diagnostic Center (Kazan, Russia), tertiary stroke center
- 2. Municipal Clinical Hospital #7 (Kazan, Russia), primary stroke center
- 3. Federal University Hospital (Kazan, Russia), primary stroke center
- 4. Perm Territorial Clinical Hospital (Perm, Russia), primary stroke center
- 5. Emergency Medical Center (Naberezhnye Chelny, Russia), primary stroke center
- 6. Leninogorsk District Hospital (Leninogorsk, Russia), primary stroke center
- 7. Nizhnekamsk District Hospital (Nizhnekamsk, Russia), primary stroke center
- 8. Arsk District Hospital (Arsk, Russia), primary stroke center

Clinical Trial Schedule

First subject's first visit: April 2018 Last subject's last visit: August 2020 (extension possible) Study report completion: September 2020

Clinical Trial Phase

IIIb

Goals of the Study

Primary objectives:

To test the hypothesis that the patients in the Cerebrolysin group would achieve reduced incidence of intracranial haemorrhagic events compared to the patients randomised to the control group

Secondary objectives:

To test the hypothesis that more patients in the Cerebrolysin group would achieve short- (day 14) and long-term (day 90) favorable functional outcome after stroke.

To evaluate hypothesis that the use of Cerebrolysin with thrombolytic therapy would be safe.

Additional objectives:

To test the hypothesis that Cerebrolysin would ameliorate ischemic injury to the brain tissue (neuroprotective effect) and stabilize blood brain barrier (BBB) permeability in stroke patients.

Methodology

A prospective, randomized, open-label, active control, multicenter, parallel-group phase IIIb pilot study.

Sample Size Calculation

Sample size calculation was performed by means of power analysis for matched case-control studies using STATA v.14.2.

The minimum detectable odds ratio (OR) for any hemorrhagic transformation (HT) was assumed as low as 0.5. The probability of any HT among controls was expected as high as 0.2. The significance level, power, and correlation of any HT between the arms were set at the values recommended by the software manual, which were 0.05, 0.8, and 0.3, respectively. As it was a pilot study, any HT was chosen for the calculation because it encompassed all types of HT. The drop-out rate is expected as low as 0.1. A 1:2 design was chosen to reduce the sample size by approximately 30%.

Thus, the expected sample size is 264: 88 patients in the Cerebrolysin group and 176 subjects in the control arms.

Inclusion Criteria:

- Confirmed diagnosis of acute ischemic stroke
- Age ≥ 18 years
- Onset of stroke symptoms within 4.5 h before initiation of rtPA administration

Exclusion Criteria:

- Current or previous intracranial hemorrhage
- Symptoms suggestive of subarachnoid hemorrhage, even if CT scan was normal
- Imaging data on admission suggestive of a brain tumor, arteriovenous malformation, brain abscess or intracerebral aneurism
- Previous history of brain tumor, intracranial aneurism or arteriovenous malformation
- Previous history of brain or spine surgery
- Acute myocardial infarction within the previous 3 months
- Major bleeding, current or within the previous 6 months
- Gastrointestinal or genitourinary bleeding within the previous 3 months
- Confirmed relapse of gastric or duodenal ulcer
- Unknown time of symptom onset
- Minor (NIHSS score <4) or severe stroke (NIHSS score >25) on admission
- Seizure at stroke onset
- Stroke or serious head trauma within the previous 3 months
- Administration of heparin within the 48 h preceding the stroke onset, with an activated partial thromboplastin time at presentation exceeding the upper limit of the normal range
- Platelet count $<100 \times 10^{9}/L$
- Systolic blood pressure >185 mm Hg or diastolic blood pressure >110 mm Hg
- Blood glucose <50 mg/dL (2.8 mmol/L) or >400 mg/dL (22.2 mmol/L)
- Oral anticoagulant treatment
- Major surgery or severe trauma within the previous 3 months
- Other major disorders associated with an increased risk of bleeding (neoplasm, bleeding diathesis, acute pancreatitis, infective endocarditis, pericarditis, severe liver and kidney failure)
- Known allergic reactions to rtPA, Cerebrolysin and its components
- Pregnancy and lactation
- Endovascular treatment

Additional Inclusion Criteria for Advanced Brain Imaging:

- No contraindications to magnetic resonance imaging (MRI) and computed tomography (CT) perfusion (CTP) study
- Stroke in the middle cerebral artery territory with a minimum diffusion-weighted imaging (DWI) lesion diameter of 20 mm on admission

Study product, dose and method of administration:

Both groups would receive a standard dose of 0.9 mg/kg recombinant tissue plasminogen activator (rtPA; alteplase) administered by IV infusion within 4.5 h after symptom onset. In addition, measures of standard care for stroke patients would be applied for both groups. Patients in the Cerebrolysin group would additionally receive 30 mL of Cerebrolysin diluted in 100 mL of normal saline administered intravenously through a separate IV line over 20 min. No treatment with other neuroprotective agents would be allowed.

Length of the Study:

Cerebrolysin treatment would be initiated simultaneously with IVT and continued once daily for 14 consecutive days. A follow-up period would be 90 days for each patient. The visits would be scheduled as follows: screening (on admission), in 24 h (visit 1), on day 7, 14, and 90 (visit 2, 3, and 4, respectively).

Endpoint evaluation:

Primary endpoint evaluation:

The study primary endpoints would be any and symptomatic HT verified on a follow-up CT scan. Symptomatic HT would be defined according to the ECASS III trial: any apparently extravascular blood in the brain or within the cranium that is associated with clinical deterioration, as defined by an increase of 4 points or more in the score on the NIHSS, or that lead to death and that is identified as the predominant cause of the neurologic deterioration.

Secondary endpoint evaluation:

Secondary endpoints would be the functional outcome measured with the National Institutes of Health Stroke Scale (NIHSS) and modified Rankin scale (mRS) as well as drug safety.

Favorable functional outcome would be defined as the mRS score of ≤ 2 at V4 (day 90).

The NIHSS score at V3 (day 14) would be considered as a marker of short-term neurological recovery.

Patients in both arms would be monitored for any adverse events (AE) at V1-3, including changes in vital signs, general and neurological condition, electrocardiogram, and routine laboratory tests (liver and kidney function tests, complete blood count).

Additional evaluation (advanced brain imaging):

At V1 and V3, a routine brain MRI on a 1.5T scanner would be acquired followed by an axial DTI scan. The DTI sequence parameters are as follows: spin-echo echo-planar imaging, repetition time = 6000 ms, echo time = 102.9 ms, field of view = 260 mm, b-value = 0 and 1000 s/mm2, matrix = 256×256 ; slice thickness = 4.5 mm, interslice gap = 1 mm, total number of slices = 24, diffusion directions = 25, scan time = $5 \min 10$ s.

The maps of fractional anisotropy (FA), axial (AD), radial (RD) and mean (MD) diffusivity would be derived from the raw DTI scans.

At V3, a brain CT perfusion (CTP) scan would be obtained using the Dankbaar's approach. It involves a cine mode CT acquisition, with a temporal sampling rate of one image every 2 s for the first 60 s. Additional gantry rotations would be performed at 90, 120, 150, 180, 210 and 240 s. Acquisition parameters are 80 kVp and 100 mA. A bolus of 40 mL iohexol (Omnipaque, GE Healthcare, USA; 300 mg/mL of iodine) would be injected into an antecubital vein at an injection rate of 5 mL/s. CT scanning would be initiated 5 s after start of the injection of the contrast bolus. A series of CT scans covered the whole brain would be obtained with 5 mm slice thickness.

The CTP data would be processed to obtain a series of the permeability surface-area product (PS) maps.

The most representative slice would be chosen for analysis in each set of images. On that slice, the infarcted area is outlined and mirrored to the contralateral hemisphere. The values of FA, AD, RD, MD, and PS would be assessed within each region of interest.

To cope with the heterogeneity of the ischemic lesions due to different locations, absolute values of the laterality index for each parameter would be calculated using the formula:

|Laterality index| = (Affected side - Unaffected side) / (Affected side + Unaffected side) × 100%.

The infarct volume was calculated on DWI (at V1) and CT (at V3) scans according to the ABC/2 method [10].

Statistical methods

This statistical plan describes biostatistical analysis scheduled at the time of development of this study design. Detailed statistical analysis plan will be developed after study completion. Analysis report with final statistical analysis plan will be integral part of the clinical trial report.

Statistical analysis would be performed using statistical software like STATA, IBM SPSS Statistics.

In this study, statistical analysis will be exploratory as the study is designed to develop a true hypothesis of efficacy and safety for the future clinical trials rather than a confirmation of any pre-specified claims. All p-values and confidence intervals may be only interpreted given exploratory nature of the analysis in consideration.

LIST OF ABBREVIATIONS

- AE Adverse Event
- ATC Anatomic Therapeutic Category
- ASPECTS The Alberta Stroke Program Early CT Score
- BBB Blood-brain barrier
- BP Blood Pressure
- CI Confidence Interval
- CT Computed Tomography
- CTP Computer tomography perfusion
- CRF Case Report Form
- GCP Good Clinical Practice
- IEC Independent Ethics Committee
- DWI Diffusion-Weighted MR Imaging
- HT Haemorrhagic transformations
- IRB Institutional Review Board
- IV Intravenous
- IVT intravenous thrombolytic therapy
- Forward) MAP-2 Microtubuli-associated Protein 2

MCA Middle Cerebral Artery

MedDRA Medical Dictionary for Drug Regulatory Affairs

- mL Milliliter
- MRI Magnetic Resonance Imaging
- mRS Modified Rankin Scale
- NIHSS National Institutes of Health Stroke Scale
- PS permeability-surface area product
- ROI Region of interest
- rtPA Recombinant Tissue Plasminogen Activator

SAE Serious Adverse Event

SAP Statistical Analysis Plan

SHT Symptomatic haemorrhagic transformations

SUSAR Serious Unexpected Severe Adverse Reaction

WHO World Health Organisation

WHO-ATC World Health Organisation: Anatomic Therapeutic Category (System of Coding Recorded Terms)

WHO-DD World Health Organisation: Drug Dictionary

BACKGROUND

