6. STUDIES

This clinical study will be pilot multicenter clinical trial. The primary endpoint will be testing hypothesis that the patients randomized to the cerebrolysin group will achieve reduced incidence of hemorrhagic transformation compared to the patients randomized to the control group. The secondary endpoints will include overall evaluation of disability and neurological status. Overall number of patients to be enrolled to both groups (1:2 ratio) will be 264.

Eight study centers will recruit patients. The treatment will be initiated within 45-270 min after stroke onset and include 14 daily intravenous infusions. The Cerebrolysin infusions would be associated with the standard baseline and rehabilitation therapy. The result will be assessed at baseline and at three visits, with the final assessment 90 days post stroke.

On admission (the screening), the patients will be evaluated for compliance with inclusion/exclusion criteria. The patients found eligible for the clinical study will be enrolled. The data to be collected at the screening will be provided in table "Schedule of the Clinical Study Procedures". These data include date and time of the stroke, modified Rankin scale rating, evaluation of medicinal products and allergic reactions, collection of medical, neurological history; physical examination, NIHSS rating, evaluation of X-ray findings and evaluation of the results of laboratory tests. Clinical diagnosis of ischemic stroke will be made. Inclusion/exclusion criteria should be further checked. Brain MRI and CT should be made at enrollment and used to rule out hemorrhagic stroke or intracranial tumor. The patients meeting these criteria and providing their informed consent will be enrolled and randomized to the Cerebrolysin group or to the control group.

By the end of the evaluation procedures the patient will receive the first dose of the study product along with thrombolytic therapy.

24-hour monitoring will be performed based on IVT protocol.

Treatment and rehabilitation diary will also be initiated as well as monitoring of adverse events and administration of co-medications.

All patients assessed by inclusion criteria will be entered in the registration log.

The list of baseline evaluations also includes NIHSS rating and modified Rankin scale rating. During the first 24 hours the patients should be monitored based on IVT protocol.

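### The 1:2 allocation is justified by a 30% saving that does not exist: it raises the total needed and loses power at a fixed 264

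*Protocol*

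**What the plan says.** The synopsis, under Sample Size Calculation, names the method: "Sample size calculation was performed by means of power analysis for matched case-control studies using STATA v.14.2". The inputs are an odds ratio ("The minimum detectable odds ratio (OR) for any hemorrhagic transformation (HT) was assumed as low as 0.5"), a control rate ("The probability of any HT among controls was expected as high as 0.2"), and significance level, power and correlation, "which were 0.05, 0.8, and 0.3, respectively". The allowance for losses is "The drop-out rate is expected as low as 0.1".

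The reason for the allocation ratio is a single sentence: "A 1:2 design was chosen to reduce the sample size by approximately 30" per cent. The next sentence uses the same term for the whole trial: "Thus, the expected sample size is 264: 88 patients in the Cerebrolysin group and 176 subjects in the control arms". Clinical Study Design, section 6 (Studies) repeats it: "Overall number of patients to be enrolled to both groups (1:2 ratio) will be 264". Nothing limits the 30% to the Cerebrolysin arm.

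The design itself is not matched. The synopsis describes parallel groups, and Clinical Study Design, section 4 describes simple randomisation from Bernoulli draws with probability 0.333.

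**The concern.** For a fixed total, a two-arm comparison is usually at or near its most efficient with equal groups. A 1:2 split should therefore need more patients in total, not 30% fewer. A saving of about 30% is, however, what one expects in the number of cases when a case-control study moves from one control per case to two. That helps where cases are scarce and controls are nearly free. Here each control patient must also be consented, given rtPA, scanned and followed to day 90.

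If the figure was carried over from that setting, the only reason given for 1:2 is wrong in direction. The trial then gives up power on its primary endpoint, and a third of its possible Cerebrolysin exposure (88 instead of 132 patients), for no saving.

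**Working it through.** **Inputs.** From the synopsis: control rate p0 = 0.2, odds ratio ψ = 0.5, α = 0.05, power 0.80, correlation 0.3. Sidedness is not stated, so two-sided is assumed (z = 1.960 and 0.842). The rate on Cerebrolysin follows as p1 = p0ψ / (1 + p0(ψ − 1)) = 0.1 / 0.9 = 0.111. Sample sizes are before the allowance for drop-out, which does not affect the comparison of ratios.

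**1. Where the 30% comes from: matched case-control formula.** I take the Stata routine to be Dupont's formula with M controls per case. The case corresponds to the Cerebrolysin patient and the exposure to any haemorrhagic transformation.

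- Covariance: 0.3 × √(0.111 × 0.889 × 0.2 × 0.8) = 0.0377.
- Probability of the event in a matched control: p+ = (p1p0 + 0.0377)/p1 = 0.539 if the case has it, and p− = ((1 − p1)p0 − 0.0377)/(1 − p1) = 0.158 if not.
- t_m = p1·C(M, m−1)·p+^(m−1)·(1−p+)^(M−m+1) + (1−p1)·C(M, m)·p−^m·(1−p−)^(M−m)
- e(ψ) = Σ m·t_m·ψ / (mψ + M − m + 1)
- v(ψ) = Σ m·t_m·ψ·(M − m + 1) / (mψ + M − m + 1)²
- Cases = [0.842·√v(0.5) + 1.960·√v(1)]² / [e(1) − e(0.5)]²

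| | M = 1 | M = 2 |
|---|---|---|
| e(1); e(0.5) | 0.0956; 0.0637 | 0.1380; 0.0906 |
| v(1); v(0.5) | 0.0478; 0.0425 | 0.0749; 0.0609 |
| Cases | 356.8 | 245.4 |
| Total patients | 2 × 356.8 = 714 | 3 × 245.4 = 736 |

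Cases fall by 1 − 245.4/356.8 = 31%, which reproduces the protocol's figure. The total rises by 736/714 − 1 = 3% (738 if 245.4 is first rounded up to 246 sets).

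The change in total depends on the correlation: +16% at 0, +7% at 0.2, +3% at 0.3 and −1% at 0.5. No value tried comes near −30%.

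**2. The design described: two independent arms.** With k controls per Cerebrolysin patient and p̄ = (p1 + k·p0)/(1 + k),

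n = [1.960·√((1 + 1/k)·p̄(1 − p̄)) + 0.842·√(p1(1 − p1) + p0(1 − p0)/k)]² / (p0 − p1)²

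- k = 1: p̄ = 0.1556; n = (1.0046 + 0.4281)² / 0.0889² = 259.8, so 260 + 260 = 520.
- k = 2: p̄ = 0.1704; n = (0.9025 + 0.3558)² / 0.0889² = 200.4, so 201 + 402 = 603.

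The Cerebrolysin arm falls by 23% and the total rises by 603/520 − 1 = 16%.

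**3. Power at a fixed 264.** Exact enumeration of all pairs of binomial counts at 11.1% versus 20%, two-sided 5%:

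| Test | 88/176 | 132/132 | Gain from 1:1 |
|---|---|---|---|
| Pearson chi-squared | 0.444 | 0.515 | 7 points |
| Likelihood ratio | 0.468 | 0.523 | 5 points |
| Firth-type Wald (0.5 added to each cell) | 0.402 | 0.500 | 10 points |

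The usual normal approximation gives 0.436 and 0.513. The gain is largest for the Firth-type test, and Firth's method is the one named under Statistical Methods. In the matched formula the corresponding powers are 35.6% and 38.1%, a difference of 2.5 points.

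**The case against.** Five points can be made for the protocol.

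- **The figure is mislabelled, not invented.** By the declared method, the Cerebrolysin arm does shrink by 31%. This is correct and explains the origin. But the protocol applies it to the sample size, which the next sentence defines as 264 in both arms.
- **The penalty is small under the protocol's own formula**, at 3% in total and about 2.5 points of power. This also stands. The direction is still opposite to the claim, and simple randomisation creates no matched sets, so 16% and 5 to 10 points are the relevant figures for this trial.
- **Unequal allocation is legitimate**, and a trial listed as having no sponsor may wish to limit treated patients. That could be a good reason, but the protocol does not give it. Going to 1:1 means 44 more courses, or 44 × 14 = 616 more infusions, which is a real burden.
- **The analysis is declared exploratory.** This softens the weight of a few points of power. It does not make the arithmetic true, and the trial was sized on a power of 0.8.
- **The larger defect is that 264 falls well short of 80% power at either ratio.** This is true, and it is a separate matter. The matched 1:2 formula gives 738 before drop-out and 822 after. Correcting the ratio recovers part of the shortfall without more recruitment, but does not close it.

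**Conclusion.** The concern holds. The sole stated reason for 1:2 is wrong in sign: the number on Cerebrolysin falls by 31% in the matched formula, while the total rises by 3% there and by 16% in the unmatched design described. At 264 patients, 1:2 costs about 5 to 10 points of power against 1:1, depending on the test, and leaves 88 rather than 132 patients exposed to Cerebrolysin.

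This rests on the protocol's 20% control rate and odds ratio of 0.5, a two-sided 5% level, and Dupont's formula as the matched method. It also takes the arms at their expected sizes, which simple randomisation will meet only approximately. A wrong reason does not by itself make 1:2 inadmissible, but as written the choice has no valid support.

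**What to change.** Preferred: randomise 1:1 with 132 per arm. Change the Bernoulli probability from 0.333 to 0.5 in Clinical Study Design, section 4. Change the 1:2 statements and arm sizes in the synopsis and in section 6, and delete the 30% sentence. This needs new text and a new allocation list; the price is 44 more Cerebrolysin courses.

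If 1:2 is kept, for example for drug supply, state that reason and replace the 30% sentence with one saying that 1:2 reduces the number of patients on Cerebrolysin but needs about 16% more patients in total than 1:1 for the same power. The 16% belongs to an unmatched comparison, so the sentence should name that basis; beside a calculation still described as matched with correlation 0.3, the figure would be 3%. This costs one sentence.

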4. MEASURES TO MINIMISE/PREVENT SYSTEMIC BIAS

Randomisation

Each eligible patient would be randomly assigned into either the Cerebrolysin or control group by simple randomization procedure. One randomization list for all centers would be issued

by generating Bernoulli variates with the probability parameter of 0.333. The Mersenne twister would be used as an active generator and the starting point was set at random.

Allocation instructions would be sealed in opaque envelopes, mixed and distributed between the centers by an independent statistician. Each envelop would be randomly picked by the investigators and would be opened after the subject's recruitment.

Investigators would enroll participants, assign them to the intervention, and assess clinically the primary and secondary endpoints. Imaging data would be evaluated locally by radiologists who would be blinded to the intervention. However, investigators and participants would not be blinded to the treatment assignment because Cerebrolysin has its particular yellowish color and it is impossible to conceal it properly.

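### The 264 patients do not give the stated 80% power: a matched formula was used for an unmatched trial, and power for an odds ratio of 0.5 is about 40–47%

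*Protocol*

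**What the plan says.** The synopsis, under Sample Size Calculation, names the method: "Sample size calculation was performed by means of power analysis for matched case-control studies using STATA v.14.2". The inputs follow. The effect to be detected is given first: "The minimum detectable odds ratio (OR) for any hemorrhagic transformation (HT) was assumed as low as 0.5". Next comes the event risk without Cerebrolysin: "The probability of any HT among controls was expected as high as 0.2". Significance level, power and correlation then take values "which were 0.05, 0.8, and 0.3, respectively". Two further statements concern attrition, "The drop-out rate is expected as low as 0.1", and the allocation ratio, "A 1:2 design was chosen to reduce the sample size by approximately 30" per cent. The result is "Thus, the expected sample size is 264: 88 patients in the Cerebrolysin group and 176 subjects in the control arms", and the total of 264 is repeated under Clinical Study Design, section 6 (Studies).

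The design itself is described elsewhere. Clinical Study Design, section 4, says each eligible patient is "randomly assigned into either the Cerebrolysin or control group by simple randomization procedure", from one Bernoulli list with probability 0.333. Statistical Methods plans univariate and multivariate logistic regression by the Firth method. No section forms matched sets or analyses them.

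**The concern.** There are two separate faults.

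- **Method.** A within-set correlation has meaning only where each treated patient is tied to particular controls. Here the two groups are independent, so the value 0.3 describes nothing in the trial.
- **Result.** An odds ratio of 0.5 from a 20% control risk is a difference of about 9 percentage points. A total of 264 looked far too small to detect that with 80% power, whichever formula is used.

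Any haemorrhagic transformation is a primary endpoint. If the power statement stands, a non-significant result will be read as coming from a trial that had four chances in five of finding a halved odds. If the true figure is below one half, missing that effect is more likely than finding it. A later trial planned from this one would inherit the error.

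**Working it through.** **Inputs (synopsis).** Control risk p0 = 0.2; OR = 0.5; alpha 0.05; power 0.8; correlation 0.3; two controls per Cerebrolysin patient; drop-out 0.1. Sidedness is not stated. I assume two-sided (z = 1.960 and 0.842) and give one-sided results as a check.

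Risk on Cerebrolysin: p1 = 0.5×0.2 / (0.8 + 0.5×0.2) = 0.1111.

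**1. The plan's own method (Dupont's matched formula, M = 2).**
- Risk in a control, given that the set's Cerebrolysin patient does or does not have the event: 0.2 ± 0.3 × (the standard-deviation term) = 0.5394 and 0.1576.
- Probability t_k that a set of three has k events: t1 = 0.2596, t2 = 0.0773.
- e(ψ) = Σ k·t_k·ψ/(kψ + M − k + 1): e(1) = 0.1380, e(0.5) = 0.0906.
- v(ψ) = Σ k·t_k·ψ(M − k + 1)/(kψ + M − k + 1)²: v(1) = 0.0749, v(0.5) = 0.0609.
- Sets = (0.842√0.0609 + 1.960√0.0749)² / (0.1380 − 0.0906)² = 245.4 with unrounded terms.

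That is 246 + 492 = 738. If the treated risk is instead solved from the conditional odds ratio (0.134), the result is 239 + 478 = 717. Both are before drop-out. The formula's power at 88 sets is 0.36–0.37. The stated figure is not reproduced.

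**2. The method that fits the design (two independent proportions, 1:2).**
- Pooled risk: (0.1111 + 2×0.2)/3 = 0.1704.
- n1 = [1.960√(0.1704×0.8296×1.5) + 0.842√(0.1111×0.8889 + 0.2×0.8/2)]² / 0.0889² = (0.9025 + 0.3558)²/0.0889² = 200.4.

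That is 201 + 402 = 603 evaluable; 603/0.9 = 670 enrolled.

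**3. Power of what is planned.** By the same approximation at 88/176: z = (√88×0.0889 − 0.9025)/0.4228 = −0.162, so power is 0.436. Exact binomial enumeration gives, by test:

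| Evaluable | Pearson | Likelihood ratio | Firth-type Wald |
|---|---|---|---|
| 88 + 176 | 0.44 | 0.47 | 0.40 |
| 79 + 158 (after 10% drop-out) | 0.41 | 0.44 | 0.37 |
| OR detectable with 80% power, 88 + 176 | 0.32 | 0.33 | 0.30 |

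**4. Sensitivity to sidedness.** A one-sided 5% test needs 157 + 314 = 471 unmatched, or 561–576 matched. Its exact power at 88/176 is 0.55–0.60.

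**5. Precision.** Expected events are 88×0.1111 = 9.8 and 176×0.2 = 35.2. SE(log OR) = √(1/9.8 + 1/78.2 + 1/35.2 + 1/140.8) = 0.388. If the true OR is 0.5, the expected 95% interval is 0.5×exp(±1.96×0.388) = 0.23 to 1.07.

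**6. Where 264 probably came from.** 264/1.1 = 240 = 80 + 160. The conditional matched variant gives 239 cases. Read as a total and split 1:2, that is 80 + 160, and multiplying by 1.1 gives exactly 88 + 176. The claimed 30% saving fits the same slip: cases fall from 344 (1:1) to 239 (1:2), or from 357 to 246, which is 30.5–31.1%. The total rises, from 688 to 717 or from 714 to 738; unmatched, it rises from 520 to 603.

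**The case against.** The strongest reply is that this is a declared pilot. The synopsis, under Statistical methods, calls the analysis exploratory and says p-values and intervals are to be read in that light. A pilot need not have 80% power, so the harm is smaller than in a confirmatory trial. That stands as mitigation. But the protocol still claims power of 0.8, words the primary objective as testing a hypothesis of fewer haemorrhagic events, and presents 264 as the output of that calculation. The label does not make the number right.

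Three technical points are also fair:

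- Two-sided testing is an assumption, since the hypothesis is worded directionally.
- The matched formula has more than one version, so 738 is not its only answer.
- The 264 includes a drop-out allowance. The like-for-like comparison is about 670 enrolled against 264, or 603 evaluable against about 237 (79 + 158).

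Each shifts a figure; none brings power near 80%.

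**Conclusion.** The concern holds. The power statement for any haemorrhagic transformation is wrong, and the method behind it does not belong to this design. The shortfall is more than half: 264 enrolled against about 670 for the effect assumed. With 264 patients, 80% power is reached only for an odds ratio of about 0.30–0.33, a much larger effect than the plan names. This rests on the protocol's own control risk and odds ratio, a two-sided 5% level, and realised group sizes of 88 and 176. The account of how 264 arose is an inference that fits both that figure and the 30% claim; the conclusion does not depend on it. Because the error concerns the stated power for a primary endpoint, it should be corrected.

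**What to change.** Keep 264 and rewrite the Sample Size Calculation section:

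- Replace the matched case-control calculation with two independent proportions at 1:2, and delete the correlation of 0.3.
- State whether the test is one- or two-sided.
- Delete the sentence on the 30% reduction. At fixed power, 1:2 allocation raises the total.
- State that, with a 20% control risk and two-sided 5% testing, 264 evaluable patients give about 40–47% power for an odds ratio of 0.5 (37–44% after 10% drop-out), and 80% power only for an odds ratio of about 0.30–0.33.
- Justify the pilot by precision instead: an expected 95% interval of about 0.23 to 1.07 if the true odds ratio is 0.5.

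The cost is one reworded section and a less favourable power statement. No patients, endpoints or analyses change. Only if 80% power for an odds ratio of 0.5 is really wanted would enrolment have to rise to about 670.
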